Prinicpal Investigators and Participating Sites	[name]. [name], Intensivist, UZ Leuven [name]. [name], Medical microbiologist, UMC Radboud Nijmegen
Medical condition or disease under investigation	Influenza-associated pulmonary aspergillosis (IAA)
Purpose of clinical trial	Study the effect of antifungal prophylaxis on the incidence of IAA in critically ill patients with severe influenza.
Primary objective	Study if antifungal prophylaxis can decrease the incidence of IAA compared to SOC in critically ill patients with severe influenza pneumonia.
Secondary objective(s)	
Trial Design	Interventional non-blinded randomized controlled multicenter study
Endpoints	The IAA incidence at ICU discharge is the primary endpoint and will be compared in patients receiving posaconazole prophylaxis with those receiving SOC. Secondary outcomes will be time to IAA diagnosis, length of ICU stay, length of hospital stay, 30-day mortality and 90-day mortality
Sample Size	50 patients in each arm
IMP, dosage and route of administration	Posaconazole, 2*300mg/d on day 1, followed by 1*300mg/d from day 2 until day 7, intravenously administrated
Active product(s)	comparator None, SOC
Maximum duration of treatment of a Subject	7 days of prophylaxis

Maximum duration of Trial	4 influenza seasons (the first two influenza seasons will be supported by MSD)
Anticipate First Patient First Visit (FPFV)	Expected 01/12/2017
Anticipate Last Patient Last Visit (LPLV)	Expected 30/03/2021

TRIAL FLOWCHART

Schedule of Events – Trial specific Procedures / Assessments

EVENTS	Screening	Randomization	Treatment Period	ICU discharge	Follow-Up Visits (phone call)
Timing (weeks)		Day 1	Day 2 - ICU discharge		Day 30 and day 90
Informed consent ^a	X				
PCR-confirmed influenza ^b	X				
Inclusion/Exclusion	X	X			
Demographics; Medical history	X				
Symptom directed physical examination	X	X	X	X	
Weight / Height	X				
Vital Signs	X	X	X	X	
Randomization		X			
Microbiology sampling	X	X ^c	X ^d	X	
Chemistry : laboratory measurements	X	X	X	X	
Radiological Assessments (CT / RX)		X	X		
Trial drug administration (max 7 days)		X	X		
IAA mycological evidence ^e	X	X	X	X	X
IAA signs and symptoms assessment	X	X	X	X	
Survival status		X	X	X	X
Adverse event (AE) assessment ^f			→		
Serious Adverse Event (SAE) assessment				→	
Concomitant Medication (CM)					

a: Informed Consent process should take place prior to all other trial-related procedures at the screening visit

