2.4 Trial Design

This study is an interventional non-blinded randomized controlled multicenter study.

- Critically ill patients with PCR-confirmed influenza (for details: see inclusion criteria) are eligible for inclusion in this study and will be randomized to or the posaconazole prophylaxis group or the SOC group. Within 48 hours after influenza diagnosis with a bronchoscopy with BAL (minimum volume of 2x20mL, 0.9% NaCl) and a with a serum galactomannan will be performed as part of routine ICU care in this type of patients. As any bronchoscopy, this bronchoscopy will only be performed if the safety of the patient will not be compromised. If an IAA-infection is suspected based on the result of this BAL ((A) *Aspergillus* cultured from BAL, or (B) a galactomannan (GM) ≥ 1 in BAL or ≥ 0.5 in serum), the patient will be withdrawn from the study and antifungal treatment will be started. The type and duration of antifungal therapy will be at the discretion of the treating physician.
- SOC further includes:
 - The treating physician can decide to perform an additional bronchoscopy with BAL between day 2 after randomisation and ICU discharge in case of respiratory deterioration and clinical suspicion of an IAA-infection. Any bronchoscopy will only be performed if the safety of the patient will not be compromised. In case of positive mycological evidence of an IAA-infection, a CT thorax without IV contrast is performed if possible. If an IAA-infection is documented, antifungal treatment will be started and - in case the IAA-infection is diagnosed before the ending of the study drug - the patient will be withdrawn from the study. Again, type and duration of antifungal therapy will be at the discretion of the treating physician.

- Oseltamivir (non-IMP) will be started at the discretion of the treating physician from the first day of ICU admission as 2*150 mg/day for a duration of 10 days. If oseltamivir had already been started up before ICU admission, oseltamivir treatment will be continued up to a total of 10 days.

*If *Aspergillus* is **only** cultured from sputum (and not from BAL) within the first 48 hours after the influenza diagnosis, the patient will not be withdrawn from the study

3 Trial Medication / Drug

Drug Name	IMP or non-IMP
Posaconazole	IMP

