3.2 Drug Accountability and Compliance

For each randomized patient 8 drug preparations (posaconazole or placebo) will be delivered by the hospital pharmacy. The amount of used and non-used posaconazole vials will be stated in a drug accountability log.

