7.1 Sample Size

Based on an estimated IAA incidence of 25% and considering a 80% reduction of the incidence (to 5%) caused by posaconazole prophylaxis and a power of 80%, a sample size calculation showed that 47 patients in each study arm are needed. Because it is impossible that the use of posaconazole will increase the

incidence of IA, a one-sided p-value was used for this sample size calculation. To include at least 100 patients in the MITT endpoint analysis, 110 patients will be included in the study (55 in each arm).

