7.2 Data Analysis

Appropriate statistical tools will be used to test for significance with respect to the primary and secondary endpoints.

Categorical variables will be reported as a percentage and continuous variables as mean \pm standard deviation (SD) or median and interquartile range (IQR), as appropriate. Differences in categorical variables will be assessed using the Chi squared test or the Fischer's Exact test and for the analysis of continuous variables the Student's t test or the Mann-Whitney U test will be used, where appropriate. P values <0.05 are considered significant. Patients that die during the trial duration will also be included in the statistical analysis.

The primary endpoint analysis will consist of a one-sided fisher-exact test in which the proportion of cases of IAA will be compared between both groups. The population included in this analysis will consist of a modified intent to treat population. This MITT population consists of all patients that received at least 1 posaco/placebo administration but excluding the patients in which a diagnosis of IAA was made on the basis of the BAL sample taken on day 1 because these patients in fact had an IAA at the day of inclusion.

8 Data handling

Patient data will be encoded: which means that personal data can only be related to an identified or identifiable person by means of a code.

Demographic, biochemical, microbiological and radiological data will be collected prospectively as a part of clinical routine. Samples will be obtained for characterization of the influenza type and for *Aspergillus* diagnosis including culture, galactomannan and PCR. These samples are part of daily routine, no additional samples for this study will be taken. All *Aspergillus* colonies will be screened for azole resistance, using an agar-based selection tool, and relevant samples, i.e. BAL fluid, will be stored for direct detection of resistance mutations by PCR. Clinical *A. fumigatus* isolates will be sent the National Mycology Reference Laboratory in Leuven (Belgium) or Nijmegen (the Netherlands) for MIC-testing and analysis of azole-resistance mutations. A blinded data review committee following a pre-defined case definition will classify patients with evidence for primary and breakthrough IAA-infection.

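### The MITT rule in 7.2 cannot be applied to the SOC arm, and its day-1 BAL exclusion misses patients withdrawn under 2.4 on serum galactomannan alone

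*Combined protocol and SAP*

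**What the plan says.** **Primary population (7.2).** Entry depends on dosing: "This MITT population consists of all patients that received at least 1 posaco/placebo administration". Baseline cases are then removed, "excluding the patients in which a diagnosis of IAA was made on the basis of the BAL sample taken on day 1". The reason given is that these patients already had IAA at inclusion.

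**Control arm.** Section 2.4 states: "This study is an interventional non-blinded randomized controlled multicenter study". The synopsis gives the active comparator as "comparator None, SOC", and 5.4 randomises to posaconazole or SOC. Placebo appears once more, in 3.2: "For each randomized patient 8 drug preparations (posaconazole or placebo) will be delivered by the hospital pharmacy".

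**Baseline withdrawal.** Section 2.4 times the sampling "Within 48 hours after influenza diagnosis with a bronchoscopy with BAL", together with a serum GM. It performs the bronchoscopy only if this is safe. It withdraws a patient with suspected IAA on any one of BAL culture, BAL GM of at least 1, or serum GM of at least 0.5. Section 5.5.2 lists BAL and serum GM on day 1 but names only mycological evidence on the day-1 BAL as the ground for withdrawal.

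**Endpoint (2.2).** Outside biopsy or autopsy, IAA needs mycology (serum GM qualifies), at least one compatible sign or symptom, and radiological abnormalities other than interstitial infiltrates. Nothing requires the evidence to arise after baseline.

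**Adjudication.** Section 2.2 has an independent committee apply the criteria at the end of the study. Section 8 adds: "A blinded data review committee following a pre-defined case definition will classify patients with evidence for primary and breakthrough IAA-infection".

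**Numbers (7.1).** 25% versus 5%, 80% power, one-sided, 47 per arm; 110 patients included (55 per arm) so that at least 100 enter the MITT analysis.

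**The concern.** The MITT rule decides who enters the only primary test, and it has two faults.

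1. **Entry.** The dosing condition has no meaning for SOC patients. They are plainly meant to be included, but the text does not say by what rule. Removing the word placebo and nothing else would drop undosed patients from the posaconazole arm while keeping every SOC patient, so the comparison would no longer be as randomised.

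2. **Exclusion.** Sections 7.2 and 2.4 describe different patients. They differ on specimen (BAL only, against BAL or serum) and on level of evidence (a diagnosis, against suspicion on mycology). A patient withdrawn on baseline serum GM alone falls between them. If the other 2.2 criteria are present, that patient counts as a primary endpoint event although the disease was there before prophylaxis could act. Section 7.2 does not tie its exclusion to the blinded committee, so in an open-label trial the treatment of these patients could be settled after outcomes are known.

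**Working it through.** **Step 1: the plan's own sample size.** Inputs from 7.1: 25%, 5%, 80% power. Section 7.1 states no alpha, so 0.05 is taken from 7.2.
- Exact one-sided Fisher test: 45 per arm is needed; power at 47 is 82.7%.
- One-sided normal formula with continuity correction: 48.
- Two-sided unpooled normal formula: (1.960 + 0.842)² × (0.25×0.75 + 0.05×0.95) / 0.20² = 7.85 × 0.235 / 0.04 = 46.1, rounded up to 47.

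The figure of 47 is reproduced to within 2. Which formula was used cannot be identified, and this point does not depend on it.

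**Step 2: the entry rule read literally.** Posaconazole at most 55, SOC 0, total at most 55, against the 7.1 target of at least 100. This shows that the rule is inoperable, not that anyone would run it.

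**Step 3: who is withdrawn under 2.4, and what 7.2 does with them.**

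| Baseline finding | 2.4 | 7.2 exclusion | 2.2 on baseline data |
|---|---|---|---|
| BAL mycology + sign or symptom + radiology | withdrawn | excluded | event, but removed |
| BAL mycology, full 2.2 criteria not met | withdrawn | not excluded | non-event |
| Serum GM only + sign or symptom + radiology | withdrawn | not excluded | **event** |
| Serum GM only, full 2.2 criteria not met | withdrawn | not excluded | non-event |

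The third row is the problem. It can arise when the BAL is negative or was not safe to perform. A compatible sign is likely at entry: 4.1(5) requires respiratory distress, and 2.2 lists dyspnea.

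**Step 4: size.** The documents give no count, so let k per arm be the number of third-row patients (assumption). The other 50 per arm follow 25% versus 5%. Events are k + Bin(50, p) out of 50 + k, tested by exact one-sided Fisher at 0.05 with all tables enumerated.

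| k per arm | SOC rate | Posaconazole rate | Apparent reduction | Power |
|---|---|---|---|---|
| 0 | 12.5/50 = 25.0% | 2.5/50 = 5.0% | 80% | 85.3% |
| 1 | 13.5/51 = 26.5% | 3.5/51 = 6.9% | 74% | 82.3% |
| 2 | 14.5/52 = 27.9% | 4.5/52 = 8.7% | 69% | 79.4% |

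If the same patients count as non-events, power stays at 85.3%.

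**Step 5: cost of the remedy, same test.**
- Undosed patients kept in, at SOC risk (assumption): 1 of 50 gives (49×5% + 25%)/50 = 5.4% and 83.1% power; 2 of 50 gives 5.8% and 80.9%.
- More baseline cases excluded, with 25% versus 5% in the rest: 45 per arm gives 80.7%; 44 gives 79.6%.

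**The case against.** **The placebo wording is template residue.** This is fair: nobody would analyse 55 treated patients against none, and 3.2 carries the same slip. A reader might infer that the primary test would be run without controls, but 7.1 plans 55 per arm and at least 100 in the analysis. What stands is that the intended SOC entry rule is not written, and the simplest edit leaves a one-arm filter. Few undosed patients are expected, because drug starts on day 1.

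**The BAL in 2.4 and the BAL in 7.2 are the same sample.** Largely right. A reader might work from 4.1(3), which allows PCR from 7 days before to 48 hours after ICU admission, and infer widely different sampling times. The flowchart attaches the 48-hour sample to the randomisation column (Day 1), 5.5.2 puts BAL and serum GM on day 1, and 4.2(5) removes transferred patients who already have mycological evidence. What remains is small: section 3.3 of the PK study measures posaconazole in this BAL, which implies that it may follow dosing.

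**A committee applies 2.2, so outcomes are not left open.** This stands for patients with BAL mycology short of the full criteria: on those data they are non-events and cost no power. It does not help with serum GM alone, because applying 2.2 faithfully makes such a patient an event.

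**The size is assumed.** Correct. Larger k could be tabulated, but 7.1 allows only 5 per arm between inclusion and MITT. Values of 3 to 5 would spend most or all of that allowance on patients whom 7.2 does not exclude.

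**Conclusion.** The rule is wrong as written and should be fixed. The entry condition cannot be applied to the control arm, and the exclusion lets through patients who meet the endpoint on baseline serum GM, against 7.2's own aim.

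The numerical effect is modest and conditional. From 85.3%, power goes to 82.3% with one such patient per arm and 79.4% with two. This assumes 25% versus 5% in the remaining 50 per arm, alpha 0.05, and equal counts in both arms.

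A reader might infer a bias favouring posaconazole. The documents do not support that: baseline cases can occur in either arm, and counting them as events dilutes the contrast. Nor does the point show that 47 per arm is wrong. Confidence is high on the two textual faults. The number of affected patients is unknown.

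**What to change.** **In 7.2:**
- Define the primary population as all randomised patients, analysed as randomised, with no dosing condition in either arm.
- Exclude, by one rule in both arms, only patients whom the blinded committee classifies as having IAA at baseline on the day-1 (2.4) BAL or the baseline serum GM.
- State that patients withdrawn under 2.4 but not classified as baseline IAA stay in the denominator and are classified by the committee under 2.2 from available data. Report their number by arm.
- Add two sensitivity analyses: all randomised patients without the exclusion, and the exclusion limited to samples taken before the first dose.

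**Elsewhere:** delete placebo from 7.2 and 3.2. Reconcile 2.4, 5.5.2 and 7.2 for analysis purposes, leaving clinical management and the 2.2 endpoint definition unchanged.

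**Cost:** protocol, SAP and committee-charter wording, with no new procedures. A few undosed posaconazole patients stay in (83.1% or 80.9% power for 1 or 2 of 50, as assumed above). Slightly more baseline cases leave the set; power stays above 80% down to 45 per arm, that is with up to 55 − 45 = 10 per arm excluded.

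**Not recommended:** barring any endpoint event that rests only on baseline specimens. That would change the 2.2 endpoint. If 1 or 2 of the 12.5 expected SOC events were of that kind, with the same share lost on posaconazole (assumption), rates become 11.5/50 = 23% versus 4.6%, or 10.5/50 = 21% versus 4.2%. Power is then 81.5% or 76.8%, at least as costly as the fault itself.

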2.2 Primary Endpoints

The incidence of IAA-infection at ICU discharge is the **primary endpoint** and will be compared for patients receiving posaconazole prophylaxis with those receiving standard of care.

A patient with **IAA-infection** is defined as a patient having mycological evidence of *Aspergillus* and at least one *Aspergillus* compatible sign or symptom and radiological abnormalities (other than interstitial infiltrates) based on chest CT, or chest X-Ray when CT imaging is not available. Mycological evidence can be provided by either (A) a positive culture of *Aspergillus* cultured from BAL sample, (B) ≥ 2 positive cultures of *Aspergillus* cultured from a sputum or a bronchial aspirate or (C) a galactomannan (GM) optical density of ≥ 1 in BAL or ≥ 0.5 in serum. Galactomannan antigen detection is conducted through sandwich enzyme-linked immunosorbent assay (ELISA) (Platelia Aspergillus; Bio-Rad Laboratories, Marnes-la-Coquette, France) and will be performed according to the instructions of the manufacturer. For the isolation of fungi, lower tract respiratory samples will be inoculated on a Sabouraud agar (2 days at 37°C and another 19 days at 30°). *Aspergillus* species are identified by their culture characteristics and morphologies.

Aspergillus compatible signs or symptoms are defined as at least one of the following:

- Worsening respiratory insufficiency in spite of proper antibiotic and ventilator support
- Dyspnea
- Haemoptysis

- Fever refractory to at least 3 days of appropriate antibiotic therapy. Recrudescent fever after a period of defervescence of at least 48 h while still on AB without apparent cause.

The presence of hyphae in lung biopsy or autopsy are also considered as sufficient evidence for IAA.

An independent review committee, consisting of a clinician and a microbiologist with substantial expertise in invasive fungal infections, will evaluate at the end of the study whether IAA-infection is present, based on the above mentioned criteria.

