4.1 Inclusion criteria

Patients eligible for inclusion in this trial have to meet **all** of the following criteria:

1. Written informed consent must be obtained from the patient or his/her legal representative prior to any study procedures
2. Adult patient (≥ 18 years)
3. PCR-confirmed influenza based on nasopharyngeal swab (NS), bronchial aspirate (BA) or broncho-alveolar lavage (BAL) within 7 days before ICU admission or within 48 hours after ICU admission.
If PCR is not available a positive result of a rapid test is required (a negative rapid test does not imply absence of influenza and thus requires confirmation by PCR)
4. Influenza symptoms present for no more than 10 days before ICU admission
5. Respiratory distress as the main reason for ICU admission. Respiratory distress will be defined as tachypnea with an respiratory rate ≥ 25 x/min and a $\text{paO}_2/\text{FiO}_2$ -ratio ≤ 300 with or without (bilateral) infiltrates.

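### The MITT exclusion in 7.2 is narrower than its stated purpose: IAA present at entry but not shown on the day-1 BAL can count as a primary event

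*Combined protocol and SAP*

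**What the plan says.** - **The exclusion (7.2).** The primary test is a one-sided Fisher exact test in a modified intention-to-treat (MITT) population, formed by "excluding the patients in which a diagnosis of IAA was made on the basis of the BAL sample taken on day 1". The reason given is "because these patients in fact had an IAA at the day of inclusion".
- **The endpoint (2.2).** Mycological evidence can be a positive BAL culture, at least two positive cultures "from a sputum or a bronchial aspirate or (C) a galactomannan (GM) optical density of ≥ 1 in BAL or ≥ 0.5 in serum". A compatible sign or symptom and radiological abnormality beyond interstitial infiltrates are also needed. No onset date and no negative baseline are required.
- **Early withdrawal (2.4).** Within 48 hours of influenza diagnosis, BAL and serum GM are done as routine ICU care. On Aspergillus in BAL culture, or "a galactomannan (GM) ≥ 1 in BAL or ≥ 0.5 in serum), the patient will be withdrawn from the study". The serum threshold appears under the result of the BAL. A footnote makes an exception for sputum alone: with the organism "cultured from sputum (and not from BAL) within the first 48 hours after the influenza diagnosis, the patient will not be withdrawn".
- **BAL is conditional (2.4).** "this bronchoscopy will only be performed if the safety of the patient will not be compromised".
- **Timing.** Section 5.5.2 lists BAL and serum GM under day 1, the day of randomisation, and flowchart footnote c is attached to the day-1 sampling cell. But that footnote and 2.4 count the 48 hours from influenza diagnosis, which inclusion criterion 3 allows "within 7 days before ICU admission or within 48 hours after ICU admission".
- **Adjudication (8).** A blinded committee "will classify patients with evidence for primary and breakthrough IAA-infection". Those classes are not defined in the text or tied to the MITT.

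**The concern.** The aim of 7.2 is to test prevention of new IAA, so infection present at inclusion should be outside the analysis. The rule that serves this aim looks at one sample type on one day, while the endpoint accepts several. A patient infected at entry whose only evidence is serum GM, or repeated sputum or aspirate cultures, or who had no day-1 BAL because bronchoscopy was unsafe, can stay in the MITT and be counted as incident.

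Prophylaxis cannot prevent an infection that already exists, so such cases move the two arms' rates towards each other. The plan expects few events: 0.25 × 50 = 12.5 and 0.05 × 50 = 2.5, about 15 in all. The background section itself describes IAA as early in the course of severe influenza. Membership of the primary population should therefore not be left to interpretation once open-label data exist.

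**Working it through.** **1. Rule against purpose, route by route.**

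| Evidence at entry | Can support IAA under 2.2 | Removed by 7.2 |
|---|---|---|
| Day-1 BAL culture or GM | Yes | Yes, if IAA is diagnosed on it |
| Serum GM ≥ 0.5 only | Yes | Ambiguous: 7.2 names only BAL; 2.4 lists serum under the BAL result |
| At least two sputum/aspirate cultures only | Yes | No |
| One sputum culture only | No | Not applicable |
| Other routes, no BAL because unsafe | Yes | No, apart from the serum ambiguity |

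The sign criterion filters little: 2.2 accepts dyspnea and inclusion criterion 5 requires respiratory distress. The radiology criterion does filter. Exclusion criterion 5 covers only transferred patients with known mycology, and criterion 7 only those already under treatment. No passage says that a patient withdrawn under 2.4, 4.4 or 5.5.2 also leaves the MITT.

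**2. The plan's own figure.** Inputs from 7.1: 25% vs 5%, 80% power, one-sided, 47 per arm. Section 7.1 gives no alpha; 0.05 is taken from 7.2.

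n = [1.645·√(2·0.15·0.85) + 0.842·√(0.25·0.75 + 0.05·0.95)]² / 0.20² = 38.4, or 39 per arm. With continuity correction, (38.4/4)·[1 + √(1 + 4/(38.4·0.20))]² = 47.8, or 48. Exact one-sided Fisher power is 82.7% at 47 per arm and 85.3% at 50. The stated 47 is reproduced within rounding, so the sample size calculation is not at fault.

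**3. Dilution.** Let r be the share of analysed patients in each arm with unexcluded entry infection. The documents do not give r; the values below are assumptions. At 50 per arm, 2%, 5% and 10% mean 1, 2.5 and 5 patients.

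- Reading A, the 25% is incident IAA only: SOC = r + (1 − r)·0.25; posaconazole = r + (1 − r)·0.05.
- Reading B, the 25% already includes r: SOC = 0.25; posaconazole = r + (0.25 − r)·0.20.

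| r | A: rates | A: relative reduction | A: power | B: rates | B: relative reduction | B: power |
|---|---|---|---|---|---|---|
| 0 | 25% vs 5% | 80% | 85.3% | 25% vs 5% | 80% | 85.3% |
| 2% | 26.5% vs 6.9% | 74% | 79.6% | 25% vs 6.6% | 74% | 76.1% |
| 5% | 28.75% vs 9.75% | 66% | 71.6% | 25% vs 9.0% | 64% | 60.5% |
| 10% | 32.5% vs 14.5% | 55% | 60.0% | 25% vs 13.0% | 48% | 35.7% |

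Power is exact, one-sided Fisher, 50 per arm. Under reading A it reaches 80% at r = 1.85%, about one patient per arm.

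**4. A single result near plan.** One-sided Fisher p at 50 per arm: 12 vs 3, 0.011. Adding one entry infection to each arm, 13 vs 4, gives 0.016; adding two, 14 vs 5, gives 0.020. Both remain significant.

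**The case against.** The strongest reply is that 7.2 is shorthand. Footnote c sits in the day-1 column and 5.5.2 places BAL and serum GM on day 1, so the sample named in 7.2 is most naturally the scheduled baseline BAL. Section 2.4 arguably makes serum GM part of that work-up. Keeping early sputum-only patients is a stated choice, and a single culture does not meet 2.2. Equal retention in both arms is conservative.

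Much of this stands. It does not settle the status of serum GM, of two or more sputum or aspirate cultures, or of patients without a BAL. A timing question also remains: a BAL timed from influenza diagnosis may fall on another day, including after the first dose, and PK 3.3 plans to measure posaconazole in it.

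Three stronger readings are tempting, and the documents do not support them:

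- A reader might combine the 7-day and 48-hour windows and infer that the BAL is commonly done up to 5 days before ICU admission. That is only arithmetic; 2.4 makes it routine ICU care.
- A reader might take 12 vs 5 (p = 0.054) as showing that two misclassified patients overturn the trial. That puts both in the posaconazole arm. It is a worst case, since the mechanism acts in both arms.
- A reader might infer a false-positive risk. Equal retention does not by itself raise type I error. If a BAL follows the first dose, exclusion could differ by arm, but the documents give neither direction nor size.

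**Conclusion.** The point holds as a gap between rule and purpose, and it should be fixed before analysis. As written, 7.2 removes IAA diagnosed on the scheduled day-1 BAL but does not clearly remove entry infection shown only by other routes that 2.2 accepts.

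The expected harm is a diluted effect and lost power. Its size rests on the assumed prevalence and on equal retention in both arms. At 2% under reading A, power is about the planned 80%, so the loss against plan is negligible; at 5% it is 72% (61% under reading B). The 10% case is an outer bound: under reading A it implies 32.5% in SOC, twice the 16% in the Dutch cohort cited in the background. Confidence in the wording gap is good; confidence in its numerical effect is limited, because the documents do not say how many patients it would touch.

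**What to change.** In 7.2:

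1. Define IAA present at entry by the 2.2 criteria, using mycological samples of any type (BAL, serum GM, at least two sputum or aspirate cultures) collected before randomisation. Add the scheduled day-1 BAL and serum GM if taken before the first dose or, in SOC, before an equivalent time point, set identically for both arms. Accept results whenever they return.
2. Have the blinded committee assign entry status from recorded sample date-times, without knowledge of arm.
3. Keep patients without a baseline BAL and classify them on their other samples.
4. Count IAA first evidenced by later samples as an event in both arms, and report by arm how many were first sampled on days 2–3.
5. Add a sensitivity analysis in all randomised patients.

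The passages on BAL timing and withdrawal (2.4, 4.4, 5.5.2, footnote c, PK 3.3) must be reconciled; no clinical rule is proposed here.

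The cost is protocol and SAP wording, recording of sample date-times, one further analysis, and outcome recording to ICU discharge for withdrawn patients unless consent is withdrawn. The downside is that entry infections first sampled after the cut-off still count as events. Because the BAL window can run past day 1, this number may not be small, hence the count by arm. The all-randomised analysis will include entry infections by construction.
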